Aim 1: Assess feasibility of the proposed RCT methodology, including recruitment, participation and attrition, treatment fidelity, safety, and problems associated with equipment.

Aim 2: Obtain estimates of variability for the primary outcome measures: time to treatment of wound complication (e.g., infection, pain, non-healing), patient's sleep, therapy adherence, and FTF clinical visits. These variability estimates are needed to calculate sample size for a subsequent larger, adequately powered RCT to compare the effects of the TOBI intervention with FTF alone.

Aim 3: Examine factors related to caregiver attitudes toward telemedicine and access to health care, as well as caregiver stress, self-efficacy, and well-being in relation to treatment outcomes. Because caregivers randomized to TOBI will be the ones delivering burn treatment under the guidance of a provider through the app, they may experience elevated stress levels and anxiety, and their self-efficacy may influence treatment. Assessing these domains will strengthen our understanding of treatment utilization and outcomes as a function of caregivers' psychological factors. We also would like to assess post-injury caregiver adjustment from a more positive perspective (e.g., personal strengths, relating to others in times of need, spiritual change, appreciation of life), a construct that is conspicuously scarce in the scientific literature on caregivers of burn-injured children. Treatment feasibility and satisfaction will also be assessed.

The proposed mHealth intervention may (1) improve the quality of and access to expert burn care for pediatric surgical patients and their families and (2) relieve the burden on burn providers by allowing them to remotely direct treatment in the patient's home. TOBI has significant clinical utility and strong potential to influence access to care and alter the doctor-patient relationship, enabling healthcare providers to prescribe the right intervention at the right dose at the right time for each patient. Findings from this study will demonstrate the feasibility of testing a scalable, low-cost intervention in a multicenter RCT.

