5.0 Inclusion and Exclusion Criteria/ Study Population

Study Population

Participants in the proposed study will be child/caregiver dyads seeking outpatient burn care at MUSC. Caregivers will be parents or legal guardians of the child participant. We expect that females and minorities will be very well represented in this study based on demographic data collected during our retrospective review of pilot data. We anticipate that 40% of youth recruited into the study will be girls. Caregivers' age may vary but the majority will be 25-45 years. Additionally, women are expected to comprise the majority (85%) of participating caregivers. Because mothers are more often the caregivers of injured patients, it is anticipated that more women will be recruited as caregiver providers than men. Participants of all racial/ethnic backgrounds will be eligible for this study. We estimate that Black or African American children and providers will comprise approximately than 50% of our sample. Given the low prevalence of individuals of Hispanic ethnicity in SC (5%) and data from our pilot study, we estimate that our sample will be comprised of approximately 5% of Hispanic youth in this study.

Inclusion Criteria for child/caregiver dyads

Participants will be eligible for enrollment if:

- (1) the patient (child) is < 18 years of age;
- (2) the patient is diagnosed with a partial thickness burn between <1% TBSA – 20% TBSA by a pediatric burn surgeon;

- (3) the burn is being treated with advanced burn dressing therapy (e.g., SilvadeneTM, PolysporinTM, ActicoatTM, MepilexTM, or MepitelTM) or skin substitutes;
- (4) the burn is evaluated by the MUSC burn team within 72 hours of injury;
- (5) the patient's caregiver (parent or legal guardian) is able to speak, hear, and understand English, as determined during study recruitment procedures;
- (6) the patient/caregiver owns and is capable of using a smart device (an Android or iOS smartphone) with permission to download TOBI app from the Google Store or AppStore;
- (7) able to comply with outpatient clinic visits.

There are no exclusion criteria. All participants who meet inclusion criteria would be eligible to participate in the study.

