10.0 Study Design / Methods

The RCT will include 64 patient/caregiver dyads recruited from the MUSC outpatient burn clinic, hospital floor, or pediatric emergency room, randomized to burn care enhanced with TOBI (n=32) or FTF standard care (n=32). After obtaining informed consent, the research staff will create a new patient record in the REDCap database and assist (if needed) the caregiver in completing the initial questionnaire battery using the REDCap survey. The baseline questionnaires, completed by the caregiver, will include the demographics form, measures about attitudes toward telemedicine, perception of healthcare access, affect, depression, anxiety, self-efficacy, and peritraumatic distress (see measures attached). All PHI will be protected by a study ID to promote confidentiality. The family will receive a ClinCard at the beginning of the study which works like a bank debit card and can be used to purchase goods or services everywhere Debit MasterCard is accepted. Each time they receive payment for participation in this study, the money will be added to the card. Families will receive \$20 for completion of baseline assessment.

At the completion of questionnaires, caregivers will be randomly assigned to treatment conditions. Stratified permuted block randomization will be used to assign patients to either the burn care enhanced with TOBI or FTF care only (32 dyads per arm). Assignment will be stratified by provider to ensure balanced enrollment across the treatment arms regardless of numbers enrolled per provider. To minimize the likelihood that the blind will be broken, i.e. the next treatment assignment can be guessed, the block size will be varied.

Chart review will be conducted within approximately 72 hours of enrollment and data will be recorded in a chart review checklist and subsequently transferred into the database (e.g., burn mechanism, % TBSA, burn location, burn depth, date of burn injury, time to medical treatment, type of first clinical encounter [burn outpatient vs. emergency department vs. hospital discharge], and type of dressing).

Patients randomized to FTF will undergo standard burn care including a return follow-up in the burn clinic on a routine basis as prescribed by the clinical burn team (e.g., at least once per week) until the burn has healed. Healing is defined as greater than 95% epithelialization of the burn wound. This will be determined by a clinician.

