focus on variability and precision of estimates rather than magnitude of effect sizes. 95% confidence intervals (CIs) of the difference in mean days to healing (or treatment change/infection) between interventions will be obtained. In addition, survival distributions and their 95% CIs will be obtained for each intervention arm using the Kaplan-Meier product limit method. Further, 95% CIs for hazard ratios will be obtained using Cox proportional hazards regression to model time to healing (treatment change) as a function of the intervention. In the future RCT, generalized linear mixed models (GLMM) will be used to obtain estimates of the variances of the clinical outcomes and the covariance structure of longitudinal measures as critical input information for determination of sample size (and hence adequate power) [82, 83]. Frequency distributions of AEs and SAEs will be used to characterize each intervention group. Analyses of caregiver data will include pre- and post-treatment group differences (TOBI vs. FTF) to understand factors related to caregiver well-being and adjustment following mHealth burn treatment and possible predictors of outcomes. These analyses may include mixed design repeated measures analyses of variance (ANOVAs) and regressions.

When the study is concluded, after 6 years all records related to the study will be destroyed. Furthermore, all staff will sign confidentiality agreements, and training sessions will emphasize the critical importance of confidentiality. The likelihood that these methods will effectively protect the confidentiality of participants is considered to be extremely high. Based on our experience with previous research projects, it is believed that these procedures will be effective in protecting confidentiality of subjects and minimizing any potential risk from participation.

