- Patients in both groups will receive an initial FTF visit either in the burn clinic, hospital, or emergency department. In routine outpatient burn care, the primary risks of burn treatment include burn wound infection, non-healing, and pain. Burn wound infection is the highest risk complication, but, fortunately, is very uncommon in pediatric burn wounds. In adults, burn wound infection approaches 5% in some studies. Data of the incidence of outpatient burn wound infection in children is incomplete, although anecdotal evidence from our practice suggests that outpatient burn wound infection is extremely uncommon. In our pilot series of 32 patients treated with TOBI, none had burn wound infection. Burn wound infection would be normally assessed on visual inspection of the wound and a clinical history of fever. In order to mitigate the small, potential risk of burn infection that is misdiagnosed by using TOBI communication, each daily digital interaction (e.g., video-conferencing, or image-transfer) will be prompted with a dialogue box asking the caregiver if the patient has had a fever in the last 24 hours. This will enhance detection of fever in a burn wound infection patient. In terms of other short-term complications measured, including non-healing or pain, if there is a suspicion that these two clinical outcome measures were inadequately treated by TOBI, the patient will be requested to make a FTF visit.
- [name] is a licensed surgeon in South Carolina and has over 12 years of experience assessing and treating patients with burn injury. He will closely supervise all study staff, and will hold weekly meetings with the team during the initial recruitment of patients. He and his partners will provide burn care using both modalities, as is their current clinical practice. All burn surgeons and therapists at MUSC will undergo training in the study procedures. All staff will have cell phone numbers where Drs. [name] and [name] will be available. [name] will coordinate his schedule with staff to ensure that he is available during any staff-patient interactions. In the rare instance where he cannot be reached, [name] will serve as the clinical backup and will follow these protocols and standards.

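### Randomisation is stratified by provider, but the between-arm analyses use neither provider, % TBSA nor baseline caregiver scores as covariates: a modest loss of precision, not a validity error

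*Combined protocol and SAP*

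**What the plan says.** Section 10.0 uses permuted blocks of varying size within provider: "Assignment will be stratified by provider to ensure balanced enrollment across the treatment arms regardless of numbers enrolled per provider". Section 14.0 says of the lead surgeon: "He and his partners will provide burn care using both modalities, as is their current clinical practice". There is therefore more than one provider, and provider is not tied to arm.

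Section 11.0 lists the between-arm analyses. Feasibility measures get chi-square tests and pooled t or Wilcoxon tests. For the clinical outcomes "95% confidence intervals (CIs) of the difference in mean days to healing (or treatment change/infection) between interventions will be obtained", with Kaplan-Meier curves by arm and a Cox model whose only named term is the intervention. The stated emphasis is to "focus on variability and precision of estimates rather than magnitude of effect sizes". Mixed models are deferred: "In the future RCT, generalized linear mixed models (GLMM) will be used to obtain estimates of the variances of the clinical outcomes".

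Eligibility in Section 5.0 runs from under 1% up to "20% TBSA by a pediatric burn surgeon". Section 10.0 also records % TBSA from the chart: "Chart review will be conducted within approximately 72 hours of enrollment".

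The Section 10.0 schedule collects telemedicine attitudes, healthcare access, PANAS, PROMIS-Depression and PROMIS-Anxiety at enrollment and at 1 month. Section 11.0 permits repeated-measures ANOVA and regression for caregiver data without stating the role of the baseline score.

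**The concern.** A factor used to balance allocation would normally also appear in the analysis. If it is left out, the benefit of balancing never reaches the reported interval, because the standard error still contains the between-provider variation that the design has removed from the comparison. A baseline measure that predicts the outcome, such as burn size for days to healing or a scale's own earlier score, likewise reduces residual variance if it is modelled.

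What is at stake is the width of the intervals for secondary outcomes. By the plan's own account, precision is what those analyses are about.

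**Working it through.** The plan gives no power, SD or target interval width to reproduce; Section 6.0 sets the sample size on pragmatic grounds.

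**Inputs from the documents.** 64 dyads, 32 per arm (Section 10.0); 95% intervals (Section 11.0); 20% attrition benchmark (Section 4.0). 32 × 0.8 = 25.6, taken as 26 per arm or 52 analysed.

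**Assumed, because the documents do not give them.** 3 to 8 providers of unequal size; the share of outcome variance explained by provider and by % TBSA (R²); the pre-post correlation ρ.

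**Starting point.** In SD units, the unadjusted half-width is t(62) × √(2/32) = 1.999 × 0.25 = 0.50 with 64 children, and 0.56 with 52.

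**Provider.** Balanced allocation removes provider differences from the difference in means, so its true variance is proportional to 1 − R². The unadjusted standard error still uses the full variance. Coverage is therefore about 2Φ(1.96/√(1 − R²)) − 1, and the width ratio (adjusted / unadjusted) is about √(1 − R²). At R² = 10%, 1.96/√0.9 = 2.066, which gives 96.1%. Simulation with blocks of 2 and 4 within provider, 64 children, 5,000 runs per setting:

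| Provider R² | Unadjusted coverage, formula | Unadjusted coverage, simulated | Width ratio, simulated |
|---|---|---|---|
| 0 | 95.0% | 94.9–95.3% | 1.001–1.009 |
| 5% | 95.6% | 95.5–95.8% | 0.975–0.983 |
| 10% | 96.1% | 96.0–96.3% | 0.948–0.955 |
| 20% | 97.2% | 97.0–97.1% | 0.894–0.900 |

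Coverage with provider in the model was 94.6–95.5%.

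**% TBSA alone.** It is not a stratification factor, so coverage without it stays nominal (simulated 94.4–95.4%). With 64 children the adjusted interval is 0.8% wider at R² = 0, and 4.5 / 9.8 / 15.6% narrower at R² = 10 / 20 / 30%.

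**Provider and % TBSA together**, which is the model proposed for healing; width ratio against unadjusted, 3 to 8 unpooled providers:

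| R² provider, % TBSA | 64 children | 52 analysed |
|---|---|---|
| 0, 0 | 1.010–1.020 | 1.018–1.041 |
| 5%, 0 | not run | 0.992–1.013 |
| 5%, 10% | 0.930–0.938 | not run |
| 10%, 20% | 0.845–0.851 | not run |

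**Caregiver scales.** With two time points, the group-by-time term of a repeated-measures ANOVA is a comparison of change scores. With equal variances σ² at both times, the variance is proportional to 2(1 − ρ)σ² for change, (1 − ρ²)σ² for ANCOVA and σ² for the 1-month score alone. The width ratios are therefore √((1 + ρ)/2) for ANCOVA against change and √(1 − ρ²) for ANCOVA against post-only.

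| ρ | ANCOVA / change, formula | ANCOVA / change, simulated (64 dyads) | ANCOVA / post-only, formula |
|---|---|---|---|
| 0.3 | 0.806 | 0.813 | 0.954 |
| 0.5 | 0.866 | 0.874 | 0.866 |
| 0.8 | 0.949 | 0.957 | 0.600 |

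ANCOVA is thus about 19 / 13 / 4% narrower than change (simulated) and about 5 / 13 / 40% narrower than post-only. Against change, the results with 52 dyads are nearly the same (0.814 / 0.876 / 0.959).

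**SD.** The simulated ratio of residual to unadjusted SD is about 0.97 / 0.95 / 0.89 at provider R² 5 / 10 / 20%. An SD on 62 df has a 95% interval of 0.85 to 1.21 times its estimate.

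**The case against.** The strongest reply is that little depends on these intervals. The primary endpoints are recruitment, attrition, fidelity, safety and technology problems; Section 1.0 disclaims hypothesis testing; no decision rule uses the width of a clinical interval. That stands, and it is why the point is minor.

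The gains are also entirely assumed. If providers differ little, the extra terms can cost more than they return: at provider R² 5% with no % TBSA effect and 52 analysed, the result runs from 0.8% narrower to 1.3% wider. That stands too, and is the reason for a pooling rule.

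On the caregiver scales, a reader might infer that the plan ignores the baseline score. It does not: repeated-measures ANOVA uses it as a repeated outcome, and ANCOVA is itself a regression, which Section 11.0 allows. The gain depends on how that permissive sentence is read, and its pattern over ρ reverses between the change-score and post-only readings. What remains is that the choice is left open, and ANCOVA is at least as precise in large samples under either reading.

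Finally, adjusting a Cox model changes what its hazard ratio estimates. That is correct, so the planned treatment-only hazard ratio is not criticised here.

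**Conclusion.** The omission is real and its effect is modest. If providers differ, the unadjusted mean-difference interval is somewhat too wide, with about 96% coverage at provider R² 10% and about 97% at 20%; if they do not, it is correct. Omitting % TBSA costs precision only, and only if burn size predicts healing. The provider count, both R² values and the pre-post correlation are all assumptions.

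A reader might go further in two ways that the documents do not support. One is that ignoring the strata makes the comparison invalid or inflates false-positive error; for the difference in means the error is in the conservative direction. The other is that Aim 2 is compromised. Aim 2 does say "These variability estimates are needed to calculate sample size for a subsequent larger, adequately powered RCT", but days to healing is not among the outcomes it names. The SD behind the stated mean-difference interval is evidently the unadjusted one, which is the cautious choice for sizing. The gap between residual and unadjusted SD also lies within the SD's own sampling interval, so nothing follows about the size of the next trial.

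Severity: minor.

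**What to change.** In Section 11.0:

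- Estimate between-arm mean differences with a linear model that includes provider, pooling sparse providers by a rule fixed in advance.
- For days to healing, add % TBSA as assessed before randomisation. Record that value at eligibility: chart review may follow assignment, and Section 5.0 does not say that the surgeon's figure is separately recorded.
- Analyse each of the five twice-measured caregiver scales by ANCOVA on its own baseline score plus provider.
- Keep the treatment-only Cox hazard ratio as planned. Label any adjusted hazard ratio as a conditional estimand.
- Optionally, report the residual SD beside the unadjusted SD, with intervals.

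The cost is SAP wording, one field at eligibility, and carrying provider from the randomisation strata into the analysis dataset. The statistical cost is a few degrees of freedom. If provider and % TBSA both have no effect, the healing interval is about 1–2% wider with 64 children and about 2–4% wider with 52 analysed and 3 to 8 unpooled providers. Pooling reduces this.

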2.0 Background

Access to expert burn care: Pediatric burn injury affects more than 120,000 patients a year, the vast majority affecting children under 6 years of age [15]. Burns are severe injuries requiring highly specialized treatments. Since 1981, the number of accredited or verified burn centers has decreased by 29%, with only 51 centers nationwide verified by the American Burn Association (ABA), and 128 self-reported centers [18, 19, 29, 30]. Unfortunately, this decline in burn centers has led to decreased access to expert burn care for many patients, particularly the rural populations. Nationally, 25%, 46%, and 68% of the US population lives within 1, 2, or 4 hours of a verified burn center; while 41%, 68%, and 91% live within a self-described burn center, with regional variation [18]. Poor access to care is evidenced by inability to pay, lack of insurance, large distances from tertiary care facilities, inadequate knowledge, limited transportation resources and time constraints, especially for working families [31]. In addition, medically-vulnerable populations are more likely to experience inferior outcomes, more likely to have fewer health care choices, and less likely to see a specialist [32]. As burn care has become regionalized, so have the resources and expertise required for high quality care. Errors and delay in treatment occur when burns are treated outside of burn centers [18, 33, 34].

Outpatient burn wound care: ~91% of serious pediatric burn injuries (those requiring medical treatment) are partial thickness burns (See Figure 2) treated in the outpatient setting, with the majority of care occurring in emergency rooms and outpatient burn or plastic surgery clinics [20]. With increasing emphasis on cost saving, larger burns are increasingly being managed in the outpatient setting [35-37]. The goals of burn wound care are to minimize pain, decrease the risk of infection, promote healthy wound healing, minimize cosmetic deformities, and preserve function [20]. Standard outpatient therapy usually lasts 10-21 days, with the majority of pediatric partial thickness burns healing by 14 days [1]. During this period, the burn wound is assessed for complications including pain, infection, non-healing, and need for operative intervention, with repeat face-to-face clinic visits, one to three times per week, depending on the practice of the burn center [38].

[figure not shown]

Figure 2. Skin Burn Types.

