4.0 Study Endpoints

Primary endpoints

- Feasibility outcomes:
 - Recruitment (ratio of how many recruited vs. consented; reasons why patients chose not to do the study);
 - Participation/attrition (percentage of those consented and retained over time vs. dropouts; or benchmark for attrition is consistent with similar studies and is 20%; reasons why patients dropped out and from which condition);
 - TOBI treatment fidelity (providers' adherence to the treatment protocol; will use a fidelity checklist each visit which will be self-rated by providers themselves and patients);
 - Safety (AE or SAE, UPs occurrence in both conditions),
 - Problems with technology (number of times problems happened, notes if TOBI did not function correctly [e.g., video breaks down]).

Secondary endpoints

- Clinical outcomes:
 - Time to treatment of wound complication (e.g., infection, pain, non-healing), patient's sleep, therapy adherence, and FTF clinical visits.
- Caregiver factors:
 - Attitudes toward telemedicine, perception of healthcare access, affect, distress/stress, depression, anxiety, self-efficacy, posttraumatic growth.
 - Satisfaction with care

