Clinical data will be collected on case report forms by the clinical care team (e.g., burn nurse, physician) and entered into the REDCap database in a coded manner by a research assistant (who is blind to the treatment condition to reduce bias during data entry) at clinically determined intervals per routine care based on clinical judgment with TOBI or FTF (see table below). The duration and number of clinical encounters for both conditions will be guided by best clinical practice and each patient's needs. On average, most burns that meet the study eligibility criteria require 2-5 visits and heal within 2-4 weeks. Case report forms will be generated with study ID only, with no identifiable PHI in order to protect patient's privacy. Data collected at intervals will include adherence to prescribed wound care, change in therapy, wound complications, day of healing, pain scores, sleep problems, unexpected return to clinic or emergency room (see Clinical Case Report Form attached). App metrics, such as number of videoconferences, number of text-messages, number of photos, and scripted messages by burn professional will be recorded by the app software and exported at the end of the study. Images of wounds will not be stored for the purposes of this study. They may be uploaded by clinical care team members into the patient's medical record as part of standard care procedures (outside of the study). Adherence to therapy will be defined as parent/patient performance of prescribed wound care through the end of treatment. Overall compliance with therapy is defined as documentation of healed burn through TOBI or FTF. Clinical data collection will continue until 1 month after the burn is diagnosed as healed by a burn physician in either condition (FTF or TOBI).

At 1-month, caregivers will be asked to complete the post-treatment questionnaires by phone or virtually using the REDCap survey, using a public link and study ID to identify their survey. This assessment will include measures about attitudes toward telemedicine, perception of healthcare access, affect, depression, anxiety, perceived stress, posttraumatic growth, treatment satisfaction, and app feasibility (TOBI only group) (see measures attached). Collected data will be entered into REDCap by the study staff. Overall, participation rate will be recorded. Families will receive \$30 following completion of post-treatment assessment.

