The following data will be collected and analyzed: Feasibility processes include recruitment and drop-out proportions, protocol adherence and patient and provider satisfaction will be assessed at 1 month. We will use 95% CIs for proportions to estimate dichotomous outcomes (proportions of subjects who agree to participate out of the number who are initially approached), the proportion who are adherent to protocol (e.g. opening messages, bi-monthly provider reports), the proportion who report satisfaction with intervention, and the proportion who exit the study prematurely (drop out). In addition, frequency distributions will be developed describing reasons for provider and patient protocol non-adherence, drop out and problems encountered such as technology glitches, etc. For the continuous feasibility measures (e.g., number of technology help requests, provider and patient satisfaction scores from patient surveys and end-of-study interview), frequency distributions and the median and mean responses (with 95% confidence intervals) will be obtained. For relevant categorical feasibility measures, chi-square tests will be used to compare the 2 groups. Pooled *t*-test (or Wilcoxon rank sum tests) will be used to compare the groups for continuous feasibility measures. We will also compare demographic and clinical characteristics for those who were eligible for study versus those who were not eligible and for those who adhered to the study protocol (study completers) versus those who did not adhere (non-adherers and drop-outs).

Quantitative analyses: In preparation for a subsequent adequately powered RCT, the planned primary clinical outcomes will be investigated. Those include variables such as time to healing, time to treatment change, and number of clinical encounters. Determination whether a wound has healed or become infected will be made at routine intervals based on clinical judgement from baseline through the day of burn healing and a final assessment 1 month after it was determined as 'healed'. Analyses for these measures

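### Section 11.0 plans Kaplan-Meier and Cox for time to treatment change without treating healing as a competing event, so either available end date leaves one of the two summaries open to misreading

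*Combined protocol and SAP*

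**What the plan says.** Section 11.0 lists the clinical outcomes to be studied for the later trial: "Those include variables such as time to healing, time to treatment change, and number of clinical encounters". Section 4.0 ranks clinical outcomes as secondary and opens that list with "Time to treatment of wound complication (e.g., infection, pain, non-healing), patient's sleep, therapy adherence, and FTF clinical visits"; treatment change is its nearest analysed counterpart.

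Three summaries follow in Section 11.0:
- a confidence interval for the "difference in mean days to healing (or treatment change/infection) between interventions will be obtained";
- by arm, "survival distributions and their 95% CIs will be obtained for each intervention arm using the Kaplan-Meier product limit method";
- hazard ratios from "Cox proportional hazards regression to model time to healing (treatment change) as a function of the intervention".

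The Kaplan-Meier sentence names no outcome, but the sentences on either side of it both include treatment change. The Cox sentence names healing and treatment change, not infection.

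No censoring rule is given. Two end dates can be read from the text. Section 11.0 has status determined "from baseline through the day of burn healing", with one last assessment a month later. Section 10.0 says: "Clinical data collection will continue until 1 month after the burn is diagnosed as healed".

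Section 10.0 schedules clinic follow-up (FTF arm) and weekly video encounters (TOBI arm) until the burn has healed. It expects most eligible burns to heal in 2-4 weeks. Section 2.0 describes outpatient therapy "with the majority of pediatric partial thickness burns healing by 14 days".

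**The concern.** Healing is the main way a child leaves scheduled wound care, and with it the setting in which a change of therapy is decided and recorded. For time to treatment change it is therefore a competing event rather than ordinary loss to follow-up.

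- **Censoring at healing.** Kaplan-Meier treats healed children as if they would have gone on to need a change at the same rate as children still unhealed. The estimated proportion with a change is then too high. The Cox hazard ratio is sound as a cause-specific rate ratio.
- **Censoring one month after healing.** The Kaplan-Meier proportion is right to about day 30. But healed children stay in the Cox risk set for a month with little or no chance of the event, so the hazard ratio also reflects how fast each arm heals.

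Aim 2 intends these estimates for the sample size of the next RCT. An inflated event proportion would make that trial expect too many events. A late-censored hazard ratio could be taken for an effect on complications when it comes from healing time. With no stated rule, the end date could also be chosen after the data are seen.

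**Working it through.** The plan has no figure to reproduce: the 64 dyads were chosen pragmatically, and no treatment-change rate is given.

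**Inputs from the documents.** 32 children per arm; most burns healing by 14 days (Section 2.0) or within 2-4 weeks (Section 10.0); weekly TOBI encounters and FTF visits at least weekly (Section 10.0).

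**Assumptions, not in the plan.** Log-normal healing time H with median m = 14 to 21 days and log-SD 0.35; constant treatment-change hazard λ = 0.005 to 0.02 per day while unhealed, and none after.

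**1. Censoring at healing, events seen as they occur.** Kaplan-Meier tends to 1 − exp(−λd). The true proportion by day d is the integral from 0 to d of λ·exp(−λt)·P(H > t) dt. At day 28:

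| λ per day | 1 − KM | True, m = 14 | Ratio | True, m = 21 | Ratio |
|---|---|---|---|---|---|
| 0.005 | 13.1% | 7.1% | 1.84 | 9.9% | 1.32 |
| 0.01 | 24.4% | 13.6% | 1.79 | 18.8% | 1.30 |
| 0.02 | 42.9% | 25.2% | 1.70 | 33.9% | 1.27 |

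At day 14 with m = 14 the pairs are 6.8% against 6.0%, 13.1% against 11.6% and 24.4% against 21.9%, a gap of at most 2.5 points.

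A Weibull healing model (shape 3) agrees. At λ = 0.02 and day 28 it gives 43% against 24% (m = 14) and 43% against 33% (m = 21).

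**2. Censoring at healing, weekly observation.** Visits fall on days 7, 14, 21 and 28. Healing is recorded at the next visit, and a change counts if it is seen at a visit before that one. Take m = 14 and λ = 0.01. The weekly event probability is q = 1 − exp(−0.07) = 0.0676. The probabilities of being unhealed after days 7, 14, 21 and 28 are 0.976, 0.500, 0.123 and 0.024.
- True: q × (0.976 + 0.932×0.500 + 0.869×0.123 + 0.811×0.024) = 10.6%.
- Kaplan-Meier steps: q×0.976 = 0.066; q×0.500/0.976 = 0.035; q×0.123/0.500 = 0.017; q×0.024/0.123 = 0.013. Then 1 − 0.934×0.965×0.983×0.987 = 12.5%.
- Relative excess: 12.5/10.6 − 1 = 18%.

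The same steps with m = 21 give 18.0% against 16.3%, or 10%. Also counting changes that arise in the same week as healing would give a larger excess.

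**3. Censoring at healing + 30 days.** No healed child is censored before day 30, so 1 − KM equals the true proportion to then (Weibull run, day 28: 0.242 against 0.242). For Cox with equal change hazards in both arms, the time in which a change can occur scales with healing time. At a common log-SD, mean healing times are in the ratio of the medians: 13/14 = 0.93 and 11/14 = 0.79. Simulated hazard ratios are about 0.94 and 0.79, and about 1.0 for equal healing. Censoring at healing gives 0.99-1.01 throughout.

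In the Weibull runs, healing hazard ratios of 0.67, 1.0, 1.5 and 2.0 give late-censored hazard ratios of 1.13, 0.99, 0.88 and 0.81. The last two match the ratios of true proportions (0.187/0.213 = 0.88; 0.172/0.212 = 0.81). This is how a subdistribution hazard ratio behaves.

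**4. Precision.** Hazards of 0.005, 0.015 and 0.03 give about 5, 13.5 and 24 events among 64 children (Weibull, m = 16). The 95% interval for the hazard ratio spans a factor of exp(1.96×2/√events) = 5.8, 2.9 and 2.2 either way.

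**The case against.** The strongest reply is that this is a feasibility trial that disclaims hypothesis testing, ranks these outcomes as secondary, and in Section 6.0 warns against sizing trials from pilot effect estimates. Intervals as wide as those above swamp the bias. With m = 14, fewer than one child per arm (32 × 0.024 = 0.8) is still unhealed at day 28, so that end of the curve says little under any estimator. All of this stands, and it limits the severity. It does not justify estimating the wrong quantity where estimation is the purpose.

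It is also fair to say that the late-censored hazard ratio is not wrong in itself. If one arm heals faster and fewer of its children need a change, a ratio below 1 reports a real difference in proportions. It misleads only if healing differs by arm and the ratio is read as a rate while unhealed.

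A reader might infer more than the documents support:
- **That Cox is planned for infection.** It is not. Infection is also assessed a month after healing, so the plan does not end that risk at healing, and the pilot had 0 of 32.
- **That nearly every child leaves by healing.** The documents say only most, or the majority.
- **That a healed child cannot have a change of therapy.** This is an assumption here. Healing means more than 95% epithelialized, and the schedule table labels the 1-month visit as end of therapy.
- **That TOBI will show a spurious benefit.** Section 3.0 reports quicker detection of healing against historical controls, with no size.
- **That 1 − KM will be the next trial's event rate.** No section says so.

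**Conclusion.** The point holds for time to treatment change. The plan names neither an end of risk nor a competing event, and each available end date leaves one planned summary open to misreading.

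With censoring at healing, the day-28 proportion is overstated by about 10-18% in relative terms if observation is weekly, which is closer to the schedule. It is overstated by about 27% to just over 80% if observation is daily. At day 14 the gap is small. With late censoring, the hazard ratio departs from 1.0 only to the extent that healing differs between arms.

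These sizes rest on assumed healing times, assumed change rates and no change after healing. The direction of the Kaplan-Meier bias does not depend on the particular rates, provided a change is less likely after healing than before. Severity is minor to moderate. Time to healing is unaffected.

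**What to change.** In Section 11.0:
- For time to treatment change, replace Kaplan-Meier with the cumulative incidence function (Aalen-Johansen), with healing as the competing event. Report it by arm with a 95% CI at fixed days such as 14 and 28.
- Keep Cox for treatment change as a cause-specific model with children censored at healing. Label it as the rate while the burn is unhealed, and report it beside the cumulative incidence.
- Report any treatment change after healing separately.
- Use the cumulative incidence, not 1 minus Kaplan-Meier, for any event rate passed to the next RCT.
- Keep Kaplan-Meier and Cox for time to healing. For infection, a simple proportion with a 95% CI is enough.

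The cost is a few sentences and one standard routine. Day of healing and change in therapy are already collected (Section 10.0). The reported event proportion will be lower than under Kaplan-Meier censored at healing. The software must support cumulative incidence, so another package may be needed if the SPSS version in use does not.
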